All allowed concomitant medications will be unchanged throughout the study. Other psychotropic medications will require a 2-4 week washout, depending on the half life of the applicable medication after the subject is deemed eligible after the screening visit. Subjects will be monitored weekly by phone for side effects or symptom worsening during the taper. Subjects randomized to the Levomilnacipran switch arm will have their SSRI tapered over 2-4 weeks after they are determined to be eligible for the study to avoid risk of discontinuation syndrome. Subjects randomized to the adjunctive quetiapine arm will have their pre-existing antidepressants continue unchanged at baseline. A flexible dose regime of levomilnacipran ER 40-120 mg/d mg per day will be followed with the FDA approved package insert. Initial titration dose will be 20 mg/d Days 1-2, increasing to 40 mg/d from Days 3-7 in week 1, flexibly dosed between 40 mg/d - 120 mg/d week 2 to week 8. FDA approved package insert guidelines will be followed for adjunctive quetiapine dosing. Adjunctive quetiapine will be started at 50 mg/d Day 1-2, increasing to 150 mg/d Days 3-7 and flexibly dosed between 150-300 mg/d week 1-8. Patients who cannot tolerate the higher dose of levomilnacipran ER or quetiapine will have their dose reduced to the lower dose per the investigator's judgment. At the end of the 8-week trial, subjects in each group will have 1-week taper of study drug. A week 9 follow up safety assessment will be performed. Subjects will be told how to safely restart their

prior medication or can be provided with a referral for continued treatment as needed.

Any new medication started during the study will be evaluated by the investigator to determine its effect on study integrity and subject safety. Subjects and primary raters will be blinded to study drug and doses.

Arm I: Levomilnacipran ER flexible dose regime (40-120 mg/d): titration dose of 20 mg po once a day from days 1-2, then 40 mg po once a day, 80mg po once a day or 120 mg once a day.

Arm II: Quetiapine flexible dose regime: 50 mg po once a day as initiating dose, 150 mg po once a day (during the period that the subjects will be titrated on 150 mg; they will be given 1-50mg tab and 1-100 mg tab with instructions to be taking once per day) (, then 300 mg po once a day.

C. Visit specific procedures and sequence:

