This is an 8-week trial with a 1 week (week 9) safety follow up visit. Visits will be planned to occur at the screening visit and weeks 0, 1, 2, 3, 4, 6, 8 and 9.

The following activities and/or assessments will be performed at/during the Screening visit (Week -4 to Week 0):

- Obtain written informed consent prior to performing any of the formal screening procedures.
- Administer the M.I.N.I
- Administer the C-SSRS, MADRS, ASEX, HAM-D, HAM-A, DSST, CGI-S, RVLTL, Spontaneous Reported AEs and Sheehan Disability
- Record demographic information
- Obtain medical and surgical and psychiatric history
- Record prior and concomitant medications
- Record vital signs (temperature, heart rate, supine and orthostatic blood pressure), body height and body weight
- Perform a complete physical examination
- Perform a 12-lead ECG

- Collect blood and urine samples for evaluation of standard laboratory safety test (chemistry, hematology, and urinalysis)
- Assess all applicable inclusion and exclusion criteria
- Schedule the baseline visit for those subjects that do not require washout of prohibited medications
- Subjects requiring washout of prohibited medication will be provided washout requirements
 - Subjects in adjunctive quetiapine arm will be permitted to continue their pre-existing antidepressants if FDA approved for depression; if not FDA approved, they will be switched to an FDA approved medication for the duration of the study but will undergo washout of other prohibited medications
- Provide instructions on washout of prohibited medication(s), including the duration of the washout period (if needed)
- Assess for and record AEs and concomitant medications

Once potential eligibility is confirmed, the investigator, or a person designated by the investigator, will contact the subject by telephone at or during the Randomization/Baseline (Week 0):

- Determine appropriate duration of the washout period of prohibited medication(s), taking into account any labeling requirements for tapering of medication dose(s), as well as the minimal washout requirements

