 - Weekly phone calls will include a Symptom Checklist, consistent with symptoms of Major Depression, suicidal risk and adverse events, which the Study Coordinator will review with the subject. Any potential concerns will be reviewed with the subject. Any potential concerns will be discussed with the PI and appropriate interventions for subject safety will be planned. The same symptom checklist and monitoring plan for the subjects will be used at the Duke and the non-Duke site.
- Assess all applicable inclusion and exclusion criteria

- Administer the C-SSRS, MADRS, ASEX, HAM-A, DSST, CGI-S, RVLTL, AES, Spontaneous Reported AEs and Sheehan Disability
- Assess for and record AEs and concomitant medications
- Dispense study medication

The following activities and/or assessments will be performed at Weeks 1 through Weeks 6:

- Assess for and record AEs and concomitant medications
- Administer the C-SSRS, MADRS, ASEX, HAM-A, DSST, CGI-S, RVLTL, AES, Spontaneous Reported AEs and Sheehan Disability
- Collect study medication and review medication compliance
- Dispense study medication

The following activities and/or assessments will be performed at Week 8: End of Study or Early Termination:

- Assess for and record AEs and concomitant medications
- Collect study medication and review medication compliance
- Record vital signs (temperature, heart rate, supine and orthostatic blood pressure), and body weight
- Collect blood and urine samples for evaluation of standard laboratory safety tests
- Administer the C-SSRS, MADRS, ASEX, HAM-A, DSST, CGI-S, RVLTL, AES, Spontaneous Reported AEs and Sheehan Disability
- Perform a 12-lead ECG

The following activities and/or assessments will be performed at the Week 9/ Safety Follow-Up Visit:

- Assess for and record AEs and concomitant medications
- Administer the C-SSRS, Spontaneous Reported AEs and the DSST

After all study assessments has been completed or if the participant completes an early term visit, the participants will be referred back to their outpatient treating physician for

psychiatric care. Participants who are uninsured will be referred to Lincoln Community Health Center or Durham Access. Results of the subject's participation will not be available to the subject before they return to their treating doctor.

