Safety and tolerability will be assessed by spontaneously reported adverse events, Columbia Suicide Severity Rating Scale (CSSRS) Arizona Sexual Experience Scale (ASEX) scores, vital signs, weight and BMI measurements and clinical laboratory assessments and evaluating reasons for dropout from the trial.

Adverse event: any untoward medical occurrence associated with the use of a drug in humans, whether or not considered drug related.

Suspected adverse reaction: any adverse event for which there is a reasonable possibility that the drug caused the adverse event

Serious Adverse Event (SAE)

A serious adverse event is one that:

- Results in death
- Is an immediate threat to life?
- Requires inpatient hospitalization, or prolongation of existing hospitalization
- Results in persistent or significant disability/incapacity
- Is a congenital anomaly or birth defect.

Causality Assessment

For all AEs, the Investigator must provide an assessment of causal relationship to the IP.

Causal relationship must be assessed by answering the following question:

Is there a reasonable possibility the IP caused the event?

Yes: There is a possible or probable relationship (i.e., there is a reasonable or strong temporal relationship, and the events are unlikely to be attributable to other drugs, underlying diseases, or other factors). Challenge and/or rechallenge (if available) is positive.

No: The relationship is unlikely or nonexistent (i.e., there is no strong temporal relationship and/or the use of other drugs, underlying diseases, or other factors provide plausible explanations for the event), or the patient did not take the IP.

Reporting of Adverse Events:

All spontaneously reported and observed adverse events will be recorded in the source and CRF documents. The Principal Investigator will inform Actavis/Forest Global Drug Safety of all SAEs within 24 hours of first knowledge of any AE that meets one of the criteria for an SAE, on a SAE report form. If, during follow-up, any nonserious AE worsens and eventually meets the criteria for an SAE, that AE will be recorded as a new SAE.

The study centers will transmit the SAE report form to the SAE [contact]) within 24 hours of first awareness of the event at the study center. Supplemental information will be submitted as soon as available and may include laboratory results,

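### Vital signs and weight are not recorded at Week 0, so their change to Week 8 cannot be divided into a pre-drug and an on-drug part

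*Combined protocol and SAP*

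**What the plan says.** Section II makes tolerability, with efficacy, part of the primary objective. Section VII (Clinical Assessments, Safety/Tolerability) lists the measures, among them "vital signs, weight and BMI measurements and clinical laboratory assessments and evaluating reasons for dropout from the trial".

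The readings are scheduled in section V.C. The screening list, "performed at/during the Screening visit (Week -4 to Week 0", includes "Record vital signs (temperature, heart rate, supine and orthostatic blood pressure), body height and body weight". The next reading is under "Week 8: End of Study or Early Termination": "Record vital signs (temperature, heart rate, supine and orthostatic blood pressure), and body weight". The Week 0 list repeats the rating scales ("Administer the C-SSRS, MADRS, ASEX, HAM-A, DSST, CGI-S, RVLTL, AES, Spontaneous Reported AEs and Sheehan Disability") and the eligibility check ("Assess all applicable inclusion and exclusion criteria"), and study drug is dispensed, but neither vital signs nor weight appears. They are also absent at Weeks 1 to 6 and at Week 9. The schedule in section XIV agrees: its vital-signs row is marked only at screening and at Week 8/ET, and weight has no row.

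Section V.B separates the arms before or around the start of drug: "Subjects randomized to the Levomilnacipran switch arm will have their SSRI tapered over 2-4 weeks after they are determined to be eligible". The quetiapine arm keeps its antidepressant. Washout of other psychotropics, also 2 to 4 weeks, can apply in either arm. Section VII (Statistical Evaluation), part C, summarizes safety outcomes descriptively by group and visit, without hypothesis tests.

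**The concern.** For MADRS, C-SSRS, ASEX and the other scales repeated at Week 0, change can be counted from the start of study drug. For weight, BMI, heart rate and blood pressure it cannot. Their only starting value comes from screening, and medication may be withdrawn between screening and first dose.

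A reader of the final tables would see change from screening to Week 8 by arm and would probably take it as change on treatment. Part of it may predate treatment, and the length of that part can differ between patients and possibly between arms. The missing reading cannot be recovered afterwards.

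**Working it through.** The plan states no figure to reproduce, so the check compares the visit lists and then works out the intervals.

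**Visit lists (V.C) against the schedule (XIV)**

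| Visit | Rating scales | Vital signs and weight, V.C | Vital-signs row, XIV |
|---|---|---|---|
| Screening | yes | yes, with height | marked |
| Week 0 | yes | no | blank |
| Weeks 1 to 6 | yes | no | blank |
| Week 8 / ET | yes | yes | marked |
| Week 9 | C-SSRS and DSST in V.C | no | blank |

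Text and table agree, so the gap is not an artefact of a broken table. Laboratory tests and ECG follow the same screening and Week 8 pattern.

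**Intervals, assuming first dose at Week 0**

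Let *g* be the weeks from the screening reading to Week 0. The screening window gives *g* = 0 to 4.

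- Screening to Week 8 = *g* + 8, that is, 8 to 12 weeks.
- Share before study drug = *g* / (*g* + 8). At *g* = 4 this is 4/12 = 33%, the ceiling for a completer.
- Switch patient whose 2 to 4 week taper is completed before Week 0: *g* = 2 to 4, interval 10 to 12 weeks, share 2/10 = 20% to 4/12 = 33%.
- Quetiapine patient with no washout: V.C allows the baseline visit to be booked directly, so *g* can be near 0, the interval about 8 weeks and the share near 0.
- Early leavers, because the last reading moves forward: with *g* = 4, exit at Week 4 gives 4/(4 + 4) = 50%, and exit at Week 2 gives 4/(4 + 2) = 67%.

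**Where the order of events matters**

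V.B ties the taper to the randomized arm. V.C and XIV put randomization and dispensing at Week 0. Three sequences are possible:

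1. Assignment is known early and the taper ends before Week 0. The figures above apply, and the interval differs by arm.
2. Randomization is at Week 0 and the taper then runs before first dose. The gap from reading to first dose could reach 4 + 4 = 8 weeks.
3. Randomization and first dose are both at Week 0 and the taper overlaps study drug. The gap is still up to 4 weeks, but it holds no SSRI taper.

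The documents do not settle which applies. In all three, the screening reading is the only one before first dose.

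**With a reading immediately before first dose**

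The gap from last pre-dose reading to first dose falls to 0. With first dose at Week 0, the on-drug interval is 8 weeks for completers in both arms.

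**The case against.** The strongest reply is that stopping the SSRI is part of what is being tested. Section II compares switching with augmenting, so a reading before the taper captures the whole switch strategy. It counts as contamination only if the target is the effect of the drug alone, which the protocol does not state. This stands, and it is why the screening reading should stay.

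A Week 0 reading would also not isolate the drug effect. Patients recently off an SSRI would still be compared with patients still on one, and later effects of stopping would remain in the switch arm. If assignment precedes the taper, a post-taper value may itself be affected by assignment, so it should not become the sole baseline. Both points stand.

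Further, safety data are described and not tested, the primary MADRS analysis is untouched, and washouts can occur in either arm. All true. These points limit the importance of the gap but do not close it: a descriptive table still needs a starting value whose meaning is clear.

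A reader might also infer that the Week 0 eligibility check is unworkable, since the exclusions cover abnormal vital signs and poorly controlled hypertension. The documents do not support that. The check covers only applicable criteria, and the vital-signs criterion is left to the investigator with no visit or threshold named.

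**Conclusion.** The scheduling gap is real and worth closing. Two named tolerability measures, and BMI which derives from one of them, have a single pre-dose value. It can be up to 4 weeks old if first dose is at Week 0, up to 33% of a completer's interval. The change to Week 8 therefore cannot be divided at the start of study drug. If the taper precedes Week 0, the interval can also differ by arm: 10 to 12 weeks for a switch patient against about 8 for a quetiapine patient without washout.

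A reader might go further and infer that the between-arm comparison of weight and blood pressure is biased by about a third. The documents do not support this. One third is a ceiling on elapsed time for completers, not a bias. No drift rate is given for either measure, so neither the size nor the direction of any distortion can be computed. That the gap contains the SSRI taper is itself conditional on an order of events that the plan leaves open.

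**What to change.** 1. Add vital signs and body weight, taken immediately before first dose, to the Week 0 list in V.C and mark them at Week 0 in XIV. Give weight its own row or name it in the vital-signs row.
2. Keep the screening reading for eligibility and as a second reference point.
3. In section VII (Statistical Evaluation), part C, state that change in vital signs, weight and BMI will be summarized descriptively from both: from screening for the whole switch-versus-augment strategy, and from the pre-dose reading for the on-drug period. Do not describe the second as the effect of the drug alone.
4. Reconcile V.B, V.C and XIV on the order of randomization, taper and first dose, so that the pre-dose reading is well defined. Which order applies is for the sponsor and investigators.

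Whether laboratory tests and ECG, or readings during treatment, should also be added is for the sponsor's clinicians.

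The cost is a few minutes at an existing visit and one more summary table. This takes Week 0 as attended in person. The lead-in to that list mentions telephone contact, but V.C counts Week 0 among the visits, and drug is dispensed there.

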Patient termination will occur if the patient experiences a clinically significant worsening of MADRS scores in two successive visits or any worsening on CSSRS on two consecutive visits, or based on clinician judgment or patient preference.

D. Concomitant Medications and Therapy:

All medications for pre-existing medical conditions will be permitted to continue unchanged provided subjects are on a stable dose of at least 12 weeks. Subjects on prohibited concomitant mood stabilizers or atypical antipsychotics will require a 2-4-week washout of the prohibited medication after the subject meets all eligibility criteria at the screening visit. Washout of prohibited medication will be determined by the $\frac{1}{2}$ life of the drug. Subjects on a minimum of 3 months of stable dose of hypnotics (e.g. zolpidem 10 mg per day or benzodiazepine dose of ≤ 2 mg per day of lorazepam or trazodone ≤ 100 mg per day) will be allowed to continue their hypnotic medication at the same dose. Over the counter medications will be permitted if in the opinion of the investigator, they are not considered to have any significant impact on the study. Any medication that has the potential to cause a clinical significant drug interaction with levomilnacipran ER or quetiapine in the judgment of the investigator will require a washout.

VI. STUDY MEDICATION

A. Description and Dispensing

a. Description and Dispensing

Levomilnacipran and quetiapine will be dispensed/administered at specified study visits.

b. Storage

All study medications will be stored in a double-locked cabinet in the Civitan Building. With available access only to the study investigator and research coordinator.

VII. CLINICAL ASSESSMENTS

Diagnostic Evaluation: The Mini-International Neuropsychiatric Interview (MINI) (version 6.6) for DSM-5 Axis I Disorders to establish diagnosis.

Study Parameters/Efficacy:

Efficacy:

The primary outcome measure will be:

Change from Baseline to end of treatment in Montgomery-Åsberg Depression Rating Scale (MADRS) Total Score.

Secondary outcome will be:

Change from baseline to end of treatment in
Clinical Global Impression Scale- Severity (CGI-S) and Improvement (CGI-I) scores
Hamilton Anxiety Rating Scale (HAM-A) scores
Hamilton Depression Rating Scale (HAM-D) scores
Sheehan Disability Scale (SDS) total score.
Scores on Digit symbol substitution test (DSST)
Scores on Rey's Verbal Learning Test (RVLT).
Scores on Apathy Evaluation Scale (AES).

Safety/Tolerability:

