Primary efficacy analysis will be conducted in the ITT population using the last-observation-carried-forward (LOCF) method. Treatment group comparisons will base on changes in MADRS from baseline to week 8/end of treatment from repeated measures ANOVA or analysis-of-covariance (ANCOVA) model containing treatment site, gender and baseline MADRS score included as a covariate.

Secondary efficacy analysis: Repeated measures ANOVA or ANCOVA models will be used to analyze change from baseline in secondary measures. Response and remission rates at end of treatment will be compared using the Cochran-Mantel- Haenszel test. No formal hypothesis testing will be performed on safety data. Safety outcomes will be summarized by treatment group and study visit (observed cases) using descriptive statistics. Any clinically significant findings among patients who terminated early will be discussed separately. All analyses will be conducted using SAS Version 9.1.3 (SAS Institute, Inc.; Cary, North Carolina). Statistical comparisons of efficacy outcomes will be 2-sided and considered significant at $P < .05$. Comparisons for secondary endpoints will be not adjusted for multiplicity.

D. Definition of Evaluable Subject (Safety and Efficacy)

Subjects will be defined as able to be evaluated by two methods. The primary method will be an intent-to-treat analysis, including those who discontinue drug due to lack of efficacy or due to side effects. The secondary method will be completer analysis.

XI: ETHICAL AND REGULATORY CONSIDERATIONS

A. Institutional Committee Approval

Duke University Health Systems Institutional Review Board (DUHS IRB) will need to approve the protocol at the Duke site. [name] site will use an external IRB (e.g. Copernicus, Western) and provide Duke with a copy of its approval.

B. Informed Consent

Participation in this study is voluntary and at no cost to the subjects. All potential participants interested in this study must be thoroughly informed of the details of the study. Prior to study participation in this trial, each subject will have an opportunity to ask questions and will sign an approved informed consent form. The signed consent forms will be filed with the investigator's copies of the Case Report Forms for each subject and a copy provided to the subject. Any subject may voluntarily withdraw from the study at any time without prejudicing treatment.

C. Document Storage and Retention

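### CGI-I is defined and analysed as a change from baseline, but it is itself a rating of improvement and has no meaningful pre-treatment value

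*Combined protocol and SAP*

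**What the plan says.** Four places in the combined protocol and SAP bear on this.

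- **VII. Clinical Assessments, outcome list.** The MADRS primary outcome is introduced by "Change from Baseline to end of treatment in". The secondary list opens with the same phrase (lower-case b), and its first item is "Clinical Global Impression Scale- Severity (CGI-S) and Improvement (CGI-I) scores". CGI-I has no definition of its own.
- **Statistical Evaluation, C. Plan of Data analysis.** For the secondary outcomes: "Repeated measures ANOVA or ANCOVA models will be used to analyze change from baseline in secondary measures". CGI-I is not excepted.
- **XIV. Schedule of Events.** One row covers CGI-I and CGI-S together. It is marked at Screening, Week 0 and Weeks 1, 2, 3, 4, 6 and 8.
- **V.C, visit-specific procedures.** The Screening list reads "Administer the C-SSRS, MADRS, ASEX, HAM-D, HAM-A, DSST, CGI-S, RVLTL, Spontaneous Reported AEs and Sheehan Disability". The lists for Week 0, Weeks 1 to 6 and Week 8 read "Administer the C-SSRS, MADRS, ASEX, HAM-A, DSST, CGI-S, RVLTL, AES, Spontaneous Reported AEs and Sheehan Disability". CGI-S is in all of them and CGI-I in none.

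The documents nowhere state what CGI-I is rated against, what a Week 0 entry should contain, that the raw score is to be analysed, or a responder category based on it.

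**The concern.** A severity score describes the patient's state on the day, so subtracting its baseline value is sensible. An improvement score is already a comparison with an earlier state. Before study drug has been given there is no on-treatment improvement to rate, so a Screening or Week 0 CGI-I has no clear content. Subtracting it from a later CGI-I gives a change in a change.

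This is more than a loose heading, because the outcome list and the analysis plan both prescribe the difference and the schedule appears to supply a baseline for it. At stake is whether the CGI-I comparison between arms has a defined meaning, and whether both sites and the analyst would arrive at the same quantity. If the plan is silent, someone has to choose after the data are in.

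**Working it through.** The plan states no figure on this point, so there is nothing to reproduce. The check sets the passages side by side and works through what the stated rule yields.

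**Inputs.** Form of the outcome: change from baseline (outcome list, analysis plan). Visits at which CGI-I is rated: Screening, Week 0 and six later visits by the schedule; none by the visit lists. Reference state for the rating: not given. First study drug: Week 0 (visit list for Week 0, and the dispensing row of the schedule).

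**Notation.** Let I0 and I8 be a patient's CGI-I at Week 0 and at Week 8 or end of treatment. The stated outcome is D = I8 − I0. Label the arms A and B.

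1. **No Week 0 rating, as in the visit lists.** I0 does not exist, so D cannot be computed and I0 cannot serve as a covariate. The visit lists read literally supply no I8 either.

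2. **Week 0 fixed at a constant c for everyone, such as no change.** Then mean D(A) − mean D(B) = [mean I8(A) − c] − [mean I8(B) − c] = mean I8(A) − mean I8(B). The contrast between arms is that of the raw score. A Week 0 CGI-I covariate has zero variance and contributes nothing. This reading is harmless, but the protocol does not state the convention.

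3. **Week 0 actually rated.** The rater needs an earlier reference, and none is given.
   - If both visits are rated against Screening, D roughly recovers the change from Week 0 to Week 8.
   - If Week 0 is rated against Screening and Week 8 against Week 0, D subtracts a rating over one interval from a rating over another and has no clear interpretation.

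   The documents do not choose between these.

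4. **ANCOVA on D with I0 as covariate.** Since D = I8 − I0, replacing D by I8 raises the coefficient of I0 by 1 and leaves the treatment coefficient unchanged. The estimate is that of the raw score adjusted for I0. It still needs an I0 for every patient. The plan leaves repeated measures ANOVA or ANCOVA open and names no covariates for the secondary models.

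So each reading fails, falls back on the raw score, or depends on a rule that is not written down.

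**The case against.** The strongest reply is that this is a wording slip with little consequence. The schedule marks at Screening and Week 0 are fully explained by CGI-S, which shares the row, and the visit lists ask for CGI-S alone there. A sensible analyst would use the raw CGI-I, and step 2 shows that a constant Week 0 value gives the same contrast. Much of this stands, and it limits the size of the point. It does not remove it: using the raw score departs from the written plan, and nothing in the documents authorises it.

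A reader might go further in three ways that the documents do not support.

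- **That the apparent effect could double with the Week 0 scoring.** This needs Week 0 rated against Screening and Week 8 against Week 0 in the same patient, and a scale range the documents do not give. If both are rated against Screening, the difference roughly removes drift before baseline.
- **That differencing inflates the SD.** The factor √(2(1 − r)) assumes equal variances at the two visits. It equals 1 at r = 0.5, since √(2 × 0.5) = 1, and exceeds 1 only below that. With a constant Week 0 the ratio is also 1. The documents give neither the variances nor r.
- **That the SSRI taper biases the comparison between arms.** V.B says "Subjects randomized to the Levomilnacipran switch arm will have their SSRI tapered over 2-4 weeks", which describes patients already randomised, while the schedule puts randomisation at Week 0. On that reading the taper follows Week 0 and cannot affect a Week 0 rating. Patients in the quetiapine arm may also wash out other prohibited medications. The timing of the taper relative to Week 0 needs reconciling in its own right, but it does not establish an artefact here.

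**Conclusion.** The point holds as a defect of definition. The outcome list and the analysis plan treat CGI-I as a state score with a baseline, and the schedule's joint row does the same. As written, the result is not computable, equals the raw score, or is a difference of two change ratings with an undefined reference.

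Its reach is one secondary outcome. The MADRS primary outcome, CGI-S and the sample size do not depend on it. No numerical bias or loss of precision can be attached to it from the documents.

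The conclusion rests on one assumption: that CGI-I rates change. The documents give no anchors or range for the scale. The assumption follows from its name, Improvement, and from its pairing with a separate Severity scale. That the visit lists omit CGI-I is a related conflict over collection. Settling it in favour of the schedule would still leave the outcome wrongly defined.

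**What to change.** Change wording in four places.

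- **Outcome list (VII. Clinical Assessments).** Separate the scales: change from Week 0 to end of treatment in CGI-S; CGI-I score at end of treatment, rated against the patient's state at Week 0.
- **Plan of Data analysis.** Except CGI-I from the change-from-baseline rule. Analyse the post-baseline CGI-I score itself, with Week 0 CGI-S as covariate.
- **Schedule of Events.** Split the joint row. Keep CGI-S at Screening and Week 0 and remove CGI-I from both.
- **Visit lists (V.C).** Add CGI-I to the Weeks 1 to 6 and Week 8 lists so that they match the schedule. Without this the replacement outcome is not collected under the visit text.

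The cost is an amendment to text. Against the schedule, it removes two ratings per patient and adds none. Against the visit lists, it adds a CGI-I rating at six visits (Weeks 1, 2, 3, 4, 6 and 8), all of which the schedule already marks.
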